### **Deaths and SAEs**

The below summaries will be provided:

- A summary of the number and percentage of participants reporting a serious TEAE
- A summary of the number and percentage of participants reporting a serious related TEAE
- A summary of the number and percentage of participants reporting a TEAE leading to death
- A summary of the number and percentage of participants reporting a serious TEAE by treatment dose at AE onset (5mg, 10/20mg and all palovarotene)

The below listings will be also provided:

- All SAEs

- All TEAEs leading to treatment discontinuation
- All Deaths

### 5.7.3 *Analysis of Secondary Endpoints*

All secondary endpoints (including derived parameters) will be listed.

#### 5.7.3.1 *FOP Physical Function Questionnaire (FOP-PFQ)*

The FOP-PFQ is a disease-specific patient-reported outcome measure of physical impairment which includes questions related to ADL and physical performance. The adult form (developed for participants  $\geq 15$  years old) will be used for all participants.

The adult FOP-PFQ consists of 28 questions which are scored on a scale of 1 to 5, with lower scores indicating that the participant has more difficulty completing those tasks. A total score, upper extremities subscore and a mobility subscore will be calculated.

- The total score: the sum of the scores from each question which will range from  $28 \times 1 = 28$  to  $28 \times 5 = 140$
- Upper extremities subscore: the sum of the scores from 15 questions (Questions 1-12, 14, 25 and 26) which will range from  $15 \times 1 = 15$  to  $15 \times 5 = 75$
- Mobility subscore: the sum of the scores from 13 questions (Questions 13, 15-24, 27 and 28) which will range from  $13 \times 1 = 13$  to  $13 \times 5 = 65$

Missing scores for individual questions will not be imputed, but they will be taken into account according to the rules described below:

- (1) If more than 20% of the questions contributing to the total score, upper extremities subscore or mobility subscore are missing, the corresponding total score will not be calculated. It will be considered as missing
- (2) If less than 20% of the questions contributing to the total score, upper extremities subscore or mobility subscore are missing, the score will be calculated by summing all observed question scores, divided by the number of questions that were answered and by multiplying this average score by the total number of questions that were meant to be answered (i.e.  $\times 28$  for the total score).

The scores will be transformed to reflect a percentage of worst score. The percentage of worst score ranges from 0% to 100% with 0% indicating the best possible function and 100% indicating the worst possible function. The table below illustrates some sample derivations of the percentage of worst scores for upper extremities:

Sample Participant	Observed FOP-PFQ Score	Lowest Possible Score	Highest Possible Score	Range of Possible Scores	Distance = Highest - Observed	Distance/ Range	Percentage of Worst Score
1	45	15	75	60	30	0.500	50.0%
2	40	15	75	60	35	0.583	58.3 %
3	35	15	75	60	40	0.667	66.7%
4	30	15	75	60	45	0.750	75.0%
5	25	15	75	60	50	0.833	83.3%

The percentage of worst scores (for total score, upper extremities subscore and mobility subscore) and changes from the inclusion visit of each subscore will be summarised at each scheduled visit with descriptive statistic on the FAS/SAS.

### 5.7.3.2 PROMIS Global Health Scale

The PROMIS Global Health Scale is a patient-reported outcome measure of physical and mental function. The adult form (developed for participants  $\geq 15$  years old) will be used for all participants. The PROMIS Global Health Scale consists of 10 questions from which two scores are calculated: the global physical health score and the global mental health score, both ranging from 4 (worse health) to 20 (better health) and are calculated as follows:

- Global physical health score: the sum of scores from Questions 3, 6, 7 and 8
- Global mental health score: the sum of scores from Questions 2, 4, 5 and 10

In the calculation of the Global Physical Health and Global Mental Health scores, the following questions will be rescaled as shown in the table below:

Questions	Raw Score	Rescaled Score
7	0	5
	1-3	4
	4-6	3
	7-9	2
	10	1
8 and 10	1	5
	2	4
	3	3
	4	2
	5	1

PROMIS=Patient Reported Outcomes Measurement Information System.

If a participant is missing any of the contributing raw scores, the corresponding score (global physical health or global mental health score) will not be calculated for that participant.

Global Physical Health scores and Global Mental Health scores will also be converted to T-scores as described in detail in Section 7.1. T-score distributions are standardised such that a value of 50 represents the average (mean) for the general population and increments of  $\pm 10$  points represent  $\pm 1$  SD away from the norm. Higher T-scores indicate better physical/mental health. A T-score  $<50$  indicates worse health than the general population, while a T-score  $>50$  indicates better health.

PROMIS Global Physical Health and Global Mental Health T-scores and changes from the inclusion visit will be summarised at each scheduled visit with descriptive statistics on the FAS/SAS.

In addition the raw scores and changes from the inclusion visit for questions 1 and 9 will be summarised separately at each scheduled visit with descriptive statistics on the FAS/SAS.

### 5.7.3.3 Cumulative Analogue Joint Involvement Scale (CAJIS)

Range of motion across the whole body will also be assessed using the CAJIS. This scale, assesses functional disability by categorising range of motion across 12 joints (both right and left shoulder, elbow, wrist, hip, knee and ankle joints) and three body regions (neck, thoracic/lumbar spine and jaw), with each joint/region assessed as: 0=normal ( $<10\%$  deficit); 1=partially impaired ( $10\%$  to  $90\%$  deficit); 2=functionally ankylosed ( $>90\%$  deficit).

The CAJIS total score is calculated as the sum of the scores of all joints/regions and ranges from 0 (no involvement) to 30 (maximally involved).

The CAJIS total score, each locations score and associated changes from the inclusion visit will be summarised at each scheduled visit with descriptive statistics on the FAS/SAS.

Ambulation will be summarised at each scheduled visit with descriptive statistics for each category as below:

- Walks only
- Walks/Wheelchair [defined as both “Walks” and “Wheelchair” marked]
- Wheelchair only

Use of assistive devices/adaptions will also be summarised at each scheduled visit with descriptive statistics for each category as below:

- Independent [defined as neither “Needs some help” or “Needs complete help” are marked]
- Needs some help
- Needs complete help

In addition a shift table of each category from the inclusion visit to each post-inclusion visit will be presented.

#### 5.7.3.4 *FOP Assistive Devices*

The use of assistive devices and adaptations for daily living will be collected using the FOP assistive devices assessment at each visit.

The number of assistive devices in each category (mobility aids, eating tools, personal care tools, bathroom aids and devices, bedroom aids and devices, home adaptions, work environment adaptions, technology adaptions, sports and recreation adaptions, school adaptions and medical therapies for daily living) and the total number of assistive devices and adaptions for daily living being used will be summarised at each scheduled visit with descriptive statistics.

In addition the change in the number of assistive devices of each category and the total number of assistive device and adaptions for daily living from the inclusion visit to each post-inclusion visit will be presented.

#### 5.7.3.5 *Healthcare Utilisation*

The use of health care services (yes/no) and their frequency in the past 6 months will be summarised at each scheduled visit with descriptive statistics. The below health services will be assessed:

- General Practitioner
- Homeopathic/Naturopathic provider
- Podiatrist
- Dentist – Orthodontist
- Occupational therapist
- Physiotherapist
- Speech therapist
- Ear, nose and throat doctor
- Psychologist/psychiatrist/counsellor
- Orthopaedic specialist
- Gastroenterologist
- Obstetrician-Gynecologist
- Dermatologist
- Pulmonologist
- Pain specialist
- Cardiologist

- Urologist
- Rheumatologist
- Neurologist
- Wound care specialist

In addition, the overall annualized rate for each healthcare service (and total healthcare services) will be summarised with descriptive statistics. The overall annualized rate will be calculated as (number of utilization during the study / duration of participant participation in the study in days) \* 365.25.

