1.3 Schedule of Activities

The schedule of activities (SoA) planned in this study are presented in [Table 1](#).

Table 1 Schedule of Activities

Assessment/Procedure	Inclusion Visit[a] Day 1			Follow-Up Visits Every 6 months (± 1 month)[b]/ EOS/EW Visit[c]	
	Procedures already performed at the parent EOS Visit that will be transferred from parent study database	Procedures already performed at the parent EOS Visit to be entered in CLIN-60120-452 eCRF by the study site	Procedures to be performed at the CLIN-60120-452 Inclusion Visit	In-clinic Visit	Remote visit
Informed consent[d]			X		
Inclusion/exclusion criteria			X		
Study intervention administration/accountability[e]			X	X	X
Baseline demographics			X		
Physical examination			X		
Participant interview[f]			X		
Pregnancy testing and childbearing potential [g]		X[a]*		X	X
Linear height and body weight [h]		X[a]*		X	X
Vital signs [i]		X[a]*		X	X
Spinal health assessment [j]		X [a]**		X	
Lung function assessments [k]			X	X	
Flare-up assessment [l]			X	X	X [m]
Additional Extra bone growth assessment (without associated flare-up)			X	X	X
CAJIS [n]	X*			X	X
C-SSRS [n] [o]			X	X	X
FOP-PFQ assessment[p] [q]	X*		X [q]***	X	X
PROMIS Global Health Scale [p][q]	X*		X [q]***	X	X
FOP assistive devices assessment [p]			X	X	X
Healthcare Utilization [p]			X	X	X
Biochemistry (amylase, lipase, AST, ALT) and triglycerides	X*				
Disease and flare-up history	X				
Prior medications	X				
Concomitant medications		X		X	X
Concomitant procedures [r]		X		X	X
AEs [s]		X		X	X

AE=adverse event; ALT=alanine aminotransferase; AST=aspartate aminotransferase; CAJIS=Cumulative Analogue Joint Involvement Scale for FOP; COVID-19=coronavirus disease 2019; C-SSRS=Columbia-Suicide Severity Rating Scale; DLCO=diffusion capacity of the lung for carbon monoxide; eCRF=electronic case report form; EOS=End of Study; EW=Early Withdrawal; FEV₁=forced expiratory volume in one second; FVC=forced vital capacity; FOP=fibrodysplasia ossificans progressiva; FOP-PFQ=FOP Physical Function Questionnaire; PROMIS=Patient Reported Outcomes Measurement Information System.

a. The Inclusion Visit should be in-clinic and corresponds ideally to the EOS Visit of the parent study (Study PVO-1A-301 or PVO-1A-202/PVO-1A-204). A maximum of one month is allowed between the two visits. For any assessments

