from the parent EOS Visit performed outside this allowed time window, assessments will need to be performed again at the Study CLIN-60120-452 Inclusion Visit (flagged with *). However, to enable continued access to the Investigational Product and rollover of participants with impaired mobility [in the case(s) when per investigator's judgement this is considered as beneficial for the participant's medical conditions], the parent EOS Visit and consenting for CLIN-60120-452 and CLIN-60120-452 Inclusion Visit can be conducted remotely. In such case(s) both parts of remote consenting used by the site – i.e. Informing/Consenting discussion and ICF signature should be agreed with the IRB/EC, and the investigator's judgement should be sufficiently documented in the patient source notes.

For the spinal health assessment, a time window of 3 months post parent visit is allowed (flagged with **).

- b. Follow-up Visits will be either in-clinic or performed remotely (e.g. at the participant's home by qualified SP in-home services, and/or via video-conference or telephone contact from clinical site personnel).
- c. The EOS/EW Visit will be ideally an in-clinic visit (or remotely when permitted by the IRB/IEC) and will occur at the time of last study intervention intake. The EOS Visit must take place before the participant transitions to commercial treatment.
- d. For participants <18 years, assent and legal guardian's consent will also be required.
- e. Palovarotene status (treated or not treated) and regimen (chronic or flare-up treatment) at the time of transition to Study CLIN-60120-452 will be collected at the Inclusion Visit. Participants will be supplied with chronic treatment as well as the appropriate dose of palovarotene to initiate flare-up treatment when a flare-up or traumatic event is confirmed by the investigator. Participants will be instructed to report potential flare-up symptoms to study site personnel, only one symptom is required to define a flare-up (see Section 6.1). In the presence of persistent flare-up symptoms, treatment may be extended in 4-week intervals until the flare-up symptoms resolve. If the participant experiences an intercurrent flare-up, or substantial high-risk traumatic event likely to lead to a flare-up, at any time during the flare-up treatment, the 12-week flare-up treatment should be restarted.

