- Technology adaptions (adapted keyboard, voice activated computer software, wireless keyboard and mouse, trackball, adapted stand for computer use, typing stick, onscreen keyboard that is not normally part of the device);
- Sports and recreation adaptions (protective helmet/body gear, adapted bicycle, other adapted recreational gear);
- School adaptions (adapted desk, adapted chair, reaching tools, special electronics for learning, adapted curriculum);
- Medical therapies for daily living (supplemental oxygen, physical therapy, hydrotherapy, energy medicine therapy, occupational therapy, lymphoedema massage treatments and wraps, wound care specialist, positive expiratory pressure mask or spirometer for breathing exercises).

8.1.5 *Healthcare Utilisation*

The healthcare utilisation information that will be collected does not rely on specific validated questionnaires, but on tailored questions which will assess the type and frequency of health services used in the past 6 months/since the last visit.

8.1.6 *Lung Function Assessments*

Lung function will be assessed at the Inclusion Visit, Follow-up Visits and at the EOS/EW Visit.

The lung function parameters of observed FVC (litres) and % predicted FVC, observed FEV₁ (litres) and % predicted FEV₁ and the absolute and predicted FEV₁/FVC ratio are obtained by spirometry.

The parameters of observed (traditional unit of mL/min/mmHg or International System of Units (SI unit) of mmol/min/kPa) ([Graham et al., 2017](#)) and % predicted DLCO is obtained by the DLCO test. This provides information on the efficiency of gas transfer from alveolar air into the bloodstream. Carbon monoxide has a high affinity for haemoglobin, and it follows the same pathway as that of oxygen to finally bind with haemoglobin. Inhaled carbon monoxide is used for this test due to its high affinity for haemoglobin which is 200-250 times that of oxygen ([Modi and Cascella, 2020](#)).

8.1.7 *Flare-up Assessment*

For each flare-up, the location of the flare-up, flare-up cause, flare-up start and stop date, whether it is ongoing, flare-up concomitant medication, symptoms and outcome (resulted in extra bone growth, restricted movement) will be collected at the Inclusion Visit (for ongoing flare-up, data from parent EOS Visit will be entered again in the Study CLIN-60120-452 eCRF), the Follow-up Visits and the EOS/EW Visits.

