## 5.2 Disposition and Analysis Sets

The following disposition summaries and listings will be provided:

- Summary table with the number and percentages of enrolled participants per country, site on the screened set
- Summary table with the number and percentage of participants screened, enrolled, treated, completed, withdrawn and reason for withdrawal on the screened set
- Summary table with the number and percentage of participants per visit on the enrolled set
- Summary table on duration of participant participation in the study on the enrolled set. The definition of the duration of participant participation is from date of consent to the last study visit or date of completion/discontinuation, whichever comes later.
- Listing of dates of visit including duration of participant participation
- Listing of withdrawal participants

In addition, the below summaries and listings will be provided:

- Summary of the number of participants within each treatment regimen subgroup
- Summary of the number and percentages of participants included in each analysis set with reasons for exclusion from each analysis set
- Listing including flag for each analysis set and reason for exclusion from each set

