#### 5.7.1.2 Handling of Dropouts and missing data

Diligent attempts will be made to limit the amount of missing data and to follow-up all enrolled participants to collect the primary and secondary efficacy endpoints for the statistical analysis.

With the exception of the QoL questionnaires, where missing data will be handled based upon the calculation of the derived scores, missing data will not be replaced but will be displayed in all relevant tables.

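### The annualised healthcare-use rate divides use known only from completed questionnaires by total participation time, and the recall period behind it is not settled

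*SAP*

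**What the plan says.** SAP 5.7.3.5 plans two kinds of summary. The first is by visit: "The use of health care services (yes/no) and their frequency in the past 6 months will be summarised at each scheduled visit". The second is an overall annualised rate for each service and for all services together, defined as "number of utilization during the study / duration of participant participation in the study in days", times 365.25. SAP 5.2 defines the duration of participation as running "from date of consent to the last study visit or date of completion/discontinuation, whichever comes later". That definition does not depend on whether any questionnaire was completed.

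The data come from a paper form filled in by the participant (Protocol 4.1) at the Inclusion Visit, each Follow-up Visit and the EOS/EW Visit (Protocol 1.3). Protocol 8.1.5 describes tailored questions on the type and frequency of services used "in the past 6 months/since the last visit". Neither document says that individual uses are dated. Follow-up Visits are six months apart with a tolerance of one month either way. The EOS/EW Visit "will occur at the time of last study intervention intake", so it is not tied to the six-month grid.

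For everything except the quality-of-life scores, SAP 5.7.1.2 says that "missing data will not be replaced but will be displayed in all relevant tables". SAP 5.7.3.5 has no rule for a missing form, for recall periods that overlap or leave gaps, or for the Inclusion form.

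**The concern.** The numerator and denominator of the rate cover different time. Uses can enter the numerator only if a completed form reports them, whereas every day of participation enters the denominator. A period without a form is therefore treated as a period without healthcare use.

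Such periods are foreseeable. EW assessments rest on reasonable efforts (Protocol 7.1 and 7.2), loss to follow-up is anticipated (Protocol 7.3), and the later-of rule in SAP 5.2 can add time after the last form.

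The two descriptions of recall add a second problem: a reader cannot tell how much time each form covers.

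Type and frequency of healthcare use is a listed secondary endpoint, and this rate is its only planned study-long summary. The error varies between participants with form completion and exit timing. If those differ by regimen, the regimen columns will differ for reasons unrelated to healthcare use.

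**Working it through.** The documents state no healthcare-use rate, so there is no figure to reproduce. The check applies the SAP formula to its expected value.

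**Inputs**
- Formula: SAP 5.7.3.5. Denominator: SAP 5.2.
- Visit spacing and EOS/EW timing: Protocol 1.3.
- Maximum follow-up: three years (Protocol 1.1), about six post-inclusion forms.
- Assumption: use is uniform at r per year. Where a rate is shown, r = 4, for illustration only. The percentages do not depend on r.

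**Formula**

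Let C be the total months of recall on the completed forms and P the months of participation. Expected uses are r × C/12, and days are 30.4375 × P. Since 365.25 / 30.4375 = 12,

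SAP rate = (r × C/12) / (30.4375 × P) × 365.25 = r × C/P, so relative bias = C/P - 1.

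**A. One form missing and not recovered (visits six months apart)**

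| Participation | Forms completed | C/P | Bias | SAP rate if r = 4 |
|---|---|---|---|---|
| 36 months | 5 of 6 | 30/36 | -16.7% | 3.33 |
| 24 months | 3 of 4 | 18/24 | -25% | 3.00 |
| 12 months | 1 of 2 | 6/12 | -50% | 2.00 |

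Replacing P by C in the denominator gives C/C = 1, so 4.0 is recovered in each row.

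**B. Does part A depend on the recall wording?**

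Partly. If the form asks about the time since the last visit, a wholly missed intermediate visit is covered by the next form: C = P and the bias is 0%. A visit that was held without the form is not recovered, because the next form starts from that visit. One such visit in six gives 30/36, again -16.7%.

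**C. All forms completed, recall a fixed six months**

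| Situation | C/P | Bias |
|---|---|---|
| Six visits 5 months apart | 36/30 | +20% |
| Five visits 7 months apart | 30/35 | -14.3% |
| EW Visit 2 months after Month 6 | 12/8 | +50% |
| EW Visit 2 months after Month 24 | 30/26 | +15.4% |

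If recall is since the last visit, none of the biases in part C arises, because consecutive periods adjoin at any spacing.

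**The case against.** **Recall may not overlap at all.** The wording in Protocol 8.1.5 can be read as six months at Inclusion and since the last visit afterwards, in parallel with the two C-SSRS versions (Protocol 8.2.2). A reader might infer that the plan double counts in any case. The documents do not support that: overlap needs a fixed six-month recall, the form itself is not in the documents, and a fixed recall also leaves gaps. What stands is that the SAP mentions only six months and the two documents need to be reconciled.

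**The Inclusion form.** A reader might infer that use before the study enters the rate. The numerator is limited to use during the study, which points to excluding it. An explicit sentence would help, but this is not a demonstrated error.

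**The missing-data rule.** A reader might see a contradiction with SAP 5.7.1.2. The formula inserts no value, and the by-visit tables show how many observations are missing (SAP 5.1.2). The rule is not breached, but it does not remove uncovered time from the denominator either.

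**The visit-window rule.** SAP 6.1 keeps the assessment closest to the scheduled day. An EW Visit at Month 8 (8 × 30.4375 = day 243.5) falls in the Month 6 window, Day 2-274, so its form could be dropped. The SAP does not say that this rule governs the study-long rate. If it did, C/P would be 6/8, or -25% instead of +50% for the same participant under fixed recall.

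**Size.** The percentages are for one affected participant, not for the study mean. The documents give no rate of missing forms. If, purely for illustration, 10% of participants with six forms each missed one, the mean rate would shift by 0.10 × 16.7% = 1.7%. Forms are also supplied at remote visits (Protocol 1.3, note p), which limits non-completion. This point stands. So does the remark that the by-visit summaries do not use this denominator.

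**Conclusion.** The denominator is wrong for data of this kind under either recall wording: it counts time for which use is unknown, and nothing in the SAP removes that time. For a participant with one unrecovered form, the rate is too low by 16.7%, 25% or 50% at three, two or one years. This assumes uniform use and six-monthly visits.

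The overcount and undercount from visit spacing (+20%, +50%, -14.3% in the cases above) are conditional on a fixed six-month recall, which the documents leave open.

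The effect on the study-level summary cannot be given without the proportion of missing forms and the exit timing. The endpoint is secondary and descriptive, so no hypothesis test or sample size is affected. The correction is nevertheless worth making, because it is cheap and the bias differs between participants.

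**What to change.** Amend SAP 5.7.3.5 before database lock:

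1. State the recall period actually printed on the form. Forms already completed cannot be changed by a SAP edit, so the analysis must follow their wording.
2. Annualise by dividing the uses on completed post-inclusion forms by the total recall time those same forms cover, instead of by total participation days. If the form asks since the last visit, each form covers the time from the previous visit held to the current one. If recall is fixed, each form contributes its own six months. A visit-to-visit denominator would not do under fixed recall: in the early-withdrawal example it still gives 12 recalled months over 8, or +50%, whereas matched recall time gives 12/12. State also how overlapping recall is handled, and whether the one-assessment-per-window rule of SAP 6.1 applies to this rate.
3. State that the Inclusion form is shown as baseline only and is not part of the on-study rate.

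The cost is one formula edit using visit dates that are already collected and listed (SAP 5.2), and slightly less person-time: 30 months instead of 36 for a participant who misses one form of six. One limit remains under fixed recall: a first follow-up form completed at five months reaches back one month before Inclusion, and a footnote should say so.
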